fMRI data analysis MRI images were preprocessed and analyzed through SPM8 (SPM8; Wellcome Trust Centre for Neuroimaging). Slice timing correction was performed for functional volumes. Functional volumes were realigned to the first volume in the experiment to correct for head motion, co-registered with the high-resolution sagittal images. The structural images were spatially normalized to a standard MNI template using the voxel-based morphometry toolbox (VBM8 <http://dbm.neuro.uni-jena.de/vbm>) and DARTEL high-dimensional warping and resampled to a 3x3x3 mm voxel size. Estimated deformation fields from warping were applied to normalize images to MNI space, and smoothed using a 5-mm FWHM Gaussian kernel. Motion scrubbing (removal of volumes) was performed based on a framewise displacement threshold of 0.3. The time course data for each voxel was band-pass filtered (0.01 to 0.10 Hz band) to capture the low-frequency spontaneous BOLD oscillations in resting state signals.

Task analysis

For the spatial navigation task, preprocessed MRI data were analyzed with the general linear model framework in SPM8. Two block regressors were modeled: allocentric and egocentric. The onsets and durations of blocks were convolved with a canonical hemodynamic response function (HRF) to create the block regressors, in addition to covariates of six image realignment parameters to reduce movement induced artifacts. In the first-level analysis for each participant, the parameter estimates of block regressors were computed at each voxel. Appropriate linear contrasts were applied to the parameter estimates to produce contrast images and statistical parametric maps (SPM t map). To evaluate activations associated with task, session, and group effects, we've

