constructed a mixed ANOVA model to test the influence of the aforementioned variables. Second-level maps were initially thresholded at whole-brain $p < .01$ to $.001$, uncorrected (extent threshold, $k = 10$). In addition to whole brain analysis, we also created a mask from activations seen in the whole brain analysis of task main effects (voxel-wise FWE $p < .05$) for use in group analyses of session effects. Specific regions of interests (ROIs) were also utilized, selected based on prior work (Hampstead et al., 2014) in regards to spatial navigation and derived from the Anatomical Automatic Labeling software (Tzourio-Mazoyer et al, 2002). These ROIs included hippocampus, superior parietal lobule, and caudate (all small volume corrected at voxel-wise FWE $p < .05$). Beta values of surviving brain activations were extracted and analyzed with ANOVA with significance threshold set at $p < .05$.

Resting state analysis

Resting state functional connectivity was first examined using a region of interest (ROI) "seed" at the stimulation site, right superior parietal lobule (rSPL), using a 10 mm radius spheres centered at MNI: (24, -60, 60). Pearson product-moment correlation coefficients were calculated between the average BOLD time course in the seed region and all other voxels in the brain. Each correlation resulted in a 3D correlation coefficient image (r-image). R-images were then transformed to z scores using a Fisher r to z transformation. Z score images from the individual functional connectivity analyses were entered into second-level random effects analyses (factorial ANOVA and t-tests) implemented in SPM8.

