We have further applied a 'data-driven' approach based on Graph Theory to analyze the functional connectivity network before and after the intervention. We've used Power's 264 anatomical coordinates to segment the brain into 264 ROIs. We included additional medial temporal and subcortical ROIs. Each ROI was defined as a 5 mm sphere centered around these coordinates. A binary grey matter mask was created through the segmentation procedure in VBM8 and the threshold probability of 0.6 (as suggested by Zalesky et. al.) was used to overlay on the normalized resting state images. The average time course signal of the grey matter voxels in each ROI was measured. Pearson's correlation between the signal time course of all possible pairs of ROIs was conducted. Correlation weights that failed the false discovery rate (FDR) threshold at $p < 0.05$ were discarded. Graph parameters, including total functional connections, network strength, and network cost were calculated.

Within each group (HC and MCI), we will use the active > sham contrast to identify regions that differ as a result of HD-tDCS. Correlations between behavioral performance (e.g., accuracy in CM) and BOLD signal will also be calculated to determine whether the altered BOLD signal is behaviorally meaningful. Because we expect functional reorganization throughout the brain within both groups as a result of HD-tDCS, we intend to use connectivity analyses to examine changes in the connectivity between the parietal cortex and the remainder of the brain.

Exploratory between group analysis will use two primary contrasts. 1) HC sham > MCI sham – which will identify disease-related differences in activation between the groups; 2) HC active > MCI active – which will examine whether the tDCS-related changes are greater in one group than the other. Taken together, these contrasts will also clarify whether tDCS restores functioning in brain regions involved in "normal" (i.e., age appropriate) navigation or whether it allows MCI patients to recruit alternative brain regions in a compensatory manner.

Additional analyses will be performed as necessary in order to fully characterize the nature of tDCS-related changes.

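### The resting-state pipeline as written describes no nuisance regression before correlation and no second-level motion term, which leaves mainly the HC versus MCI connectivity comparisons open to residual motion and physiological signal

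*Combined protocol and SAP*

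**What the plan says.** The fMRI data analysis section gives the preprocessing in order: slice timing correction, realignment ("Functional volumes were realigned to the first volume in the experiment to correct for head motion"), co-registration, normalisation, 5-mm smoothing, scrubbing ("Motion scrubbing (removal of volumes) was performed based on a framewise displacement threshold of 0.3") and filtering ("The time course data for each voxel was band-pass filtered (0.01 to 0.10 Hz band").

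The Resting state analysis section then moves to the correlations. For the right superior parietal seed, "Pearson product-moment correlation coefficients were calculated between the average BOLD time course in the seed region and all other voxels in the brain". The Fisher z images "were entered into second-level random effects analyses (factorial ANOVA and t-tests) implemented in SPM8". For the graph analysis, "The average time course signal of the grey matter voxels in each ROI was measured" and then "Pearson's correlation between the signal time course of all possible pairs of ROIs was conducted". Neither branch names a nuisance regressor, and the second-level models name no motion covariate.

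The Task analysis section does name one: the first-level model has its block regressors "in addition to covariates of six image realignment parameters to reduce movement induced artifacts".

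**The concern.** Realignment corrects head position but does not remove the signal change that movement leaves in the time series. Scrubbing drops volumes above a displacement threshold and leaves smaller movements in the data. The band-pass removes what lies outside its band, not nuisance signal inside it. The grey-matter mask in the graph analysis selects which voxels are averaged and regresses nothing.

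Nuisance signal that two regions share with the same sign raises their correlation. If its share differs between HC and MCI, the difference can appear as a diagnostic effect in the seed maps. It can also appear in total functional connections and network strength, which accumulate over many edges. The plan expects reorganisation throughout the brain, and a diffuse nuisance effect could look much like that.

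**Working it through.** The plan states no figure on this point, so there is none to reproduce. The check has three parts.

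**1. Task and resting pipelines compared.**

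| Step | Task data | Resting data |
|---|---|---|
| Realignment | yes | yes |
| Six realignment parameters as regressors | yes | not described |
| White-matter or CSF regression | not described | not described |
| Second-level motion term | not described | not described |

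The option in Statistical Design to add confounders as covariates refers to the behavioural ANOVA, so it does not fill the gap.

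**2. What the filter lets through.** The resting TR is 900 ms (fMRI Scanning).
- Sampling rate is 1/0.9 = 1.111 Hz; Nyquist is 0.556 Hz.
- Breathing at an assumed 0.2-0.3 Hz is below Nyquist and outside 0.01-0.10 Hz, so its primary frequency is filtered out.
- A cardiac frequency h near the sampling rate aliases to |h − 1.111|. This falls in the band for h from 1.011 to 1.101 Hz and from 1.121 to 1.211 Hz. Multiplied by 60, these are 60.7-66.1 and 67.3-72.7 beats/min. At those heart rates the cardiac signal passes the filter.

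**3. Illustrative size for a group contrast.** Suppose a shared nuisance signal explains a fraction f of the in-band variance in both series, with the same sign. Then

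observed r = (1 − f) × true r + f,

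so a true zero becomes f. Between two groups the bias in Fisher z is d = atanh(f₂) − atanh(f₁). For a two-sided two-sample t-test at 5% with n per group, the noncentrality is d / (SD × √(2/n)).

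These inputs are assumptions, as the documents give none of them: f as shown, SD of z 0.15 or 0.20, and n = 20 or 30. Thirty per group is the most that an even split of the enrolment ceiling of 60 allows. Twenty allows for a shortfall or for participants enrolled without MRI (Participants).

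Example: f of .05 versus .10 gives d = 0.1003 − 0.0500 = 0.0503. With SD 0.15 and n = 30, the noncentrality is 0.0503 / (0.15 × 0.2582) = 1.30 and the rejection rate is 24.8%.

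| f₁ versus f₂ | d | n = 20, SD 0.20 / 0.15 | n = 30, SD 0.20 / 0.15 |
|---|---|---|---|
| equal | 0 | 5% / 5% | 5% / 5% |
| .05 versus .07 | 0.020 | 6.1% / 7.0% | 6.7% / 8.0% |
| .05 versus .10 | 0.050 | 12% / 18% | 16% / 25% |
| .05 versus .15 | 0.101 | 34% / 55% | 49% / 73% |

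An idealised simulation (500 band-passed volumes, 400 repeats, true r = 0) agrees with the formula. For f of 0.10, 0.20 and 0.30 the mean r was 0.107, 0.211 and 0.302. After regressing out a perfectly measured nuisance signal it was 0.006, 0.018 and 0.003. Real regressors are imperfect, so the real gain would be smaller.

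**The case against.** **The text is silent; it does not say that regression was omitted.** A reader might infer that the correlations were run without it. The documents do not establish that: the resting description is terse in places (the displacement threshold has no unit, and no scan length is given), and a step may have been done and not reported. This stands, and the request must allow for it. It does not remove the point, because the same section names motion regressors where it uses them. Anyone following the plan as written would not regress.

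**The plan does handle motion.** It has realignment and scrubbing, and without a unit for 0.3 one cannot say how much movement scrubbing leaves. This also stands. The concern is limited to motion below the threshold and to physiological signal.

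**The stimulation contrast is largely protected.** A reader might infer that residual motion could pass for an HD-tDCS effect. Under Study Procedures, active and sham are given in randomised order within person, inside each diagnostic group, with blinding. Stable personal motion and physiology largely cancel. Systematic bias requires stimulation itself to change motion or physiology, and the documents give no evidence that it does.

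**The between-group analysis is secondary.** The plan labels it exploratory, and its named contrasts concern task activation, where motion regressors are present. Aim 2 predicts BOLD change and does not name resting connectivity. This lowers the weight of the point. A group term can still enter the resting factorial ANOVA, and group differences in graph measures remain exposed.

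**The offset need not be uniform.** Nuisance signal need not load with the same sign in every region, and cardiac aliasing depends on heart rate. It would be too strong to say that every correlation is inflated.

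**Conclusion.** The point holds as a moderate one about the connectivity analyses; it does not touch the behavioural analysis. As written, the resting pipeline leaves sub-threshold motion and in-band physiological signal in the correlations, and nothing at the second level adjusts for them. The exposed comparison is HC versus MCI.

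The size depends wholly on assumed fractions. Quoting only the 16-25% or 49-73% rates at 30 per group would mislead, since those need a two- or three-fold imbalance in shared nuisance between the groups. A small imbalance, .05 versus .07, gives 6-8%, and equal fractions give no bias. The point still merits action, because the plan offers no safeguard against an imbalance and the remedy is cheap.

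**What to change.** Before correlation, regress the six realignment parameters and the mean white-matter and CSF signals from each resting series, for both the seed and the graph analyses. Take the tissue masks from the existing VBM8 segmentation, and extract the signals from unsmoothed data so that smoothing does not mix grey-matter signal into them. Apply the same band-pass and scrubbing to the regressors. Add each session's mean framewise displacement as a second-level nuisance term. If the regression was already done, state it in the plan.

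The cost is a re-run of the resting pipeline and some lost degrees of freedom per scan. No new data are needed, since the realignment parameters and the segmentation already exist.

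### No corrected whole-brain threshold is set for stimulation or group effects: maps use an uncorrected range (p<.01 to .001, k=10) with no rule for choosing, and the follow-up beta ANOVA names neither route nor effect

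*Combined protocol and SAP*

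**What the plan says.** Under *Task analysis*, the second-level mixed ANOVA has this stated purpose: "To evaluate activations associated with task, session, and group effects". Three routes to a result follow.

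- **Whole brain:** "Second-level maps were initially thresholded at whole-brain $p < .01$ to $.001$, uncorrected", with k = 10. The word *initially* is not followed by a final rule.
- **Task mask:** "we also created a mask from activations seen in the whole brain analysis of task main effects", defined at voxel-wise FWE p<.05 and used for session effects. No threshold is given for the tests run inside it.
- **A priori ROIs:** "These ROIs included hippocampus, superior parietal lobule, and caudate (all small volume corrected at voxel-wise FWE" p<.05).

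The section ends: "Beta values of surviving brain activations were extracted and analyzed with ANOVA with significance threshold set at" p<.05.

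The contrasts are set out after *Resting state analysis*. One is within group: "Within each group (HC and MCI), we will use the active > sham contrast to identify regions" that stimulation changes. The others compare HC with MCI, once under sham and once under active stimulation: "Exploratory between group analysis will use two primary contrasts". None of these is tied to a threshold or a route.

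Preprocessing (*fMRI data analysis*) gives 3 mm voxels and images "smoothed using a 5-mm FWHM Gaussian kernel". *Participants* allows up to 60 people, HC and MCI together, with no split and no number scanned.

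**The concern.** Two things are left open.

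First, the plan lets the analyst use any voxel threshold between p<.01 and p<.001 without correction. Outside the three ROIs, nothing corrected stands behind a stimulation or group effect. The plan's questions do reach outside those ROIs: it expects reorganization across the brain and asks whether MCI patients compensate by using other regions. At the loose end of the range, a region is expected to appear even if stimulation does nothing.

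Second, the beta ANOVA does not say which route an activation has to survive, or whether task, session, group or an interaction is tested. Some ways of filling that gap are harmless and some are misleading.

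At stake is Aim 2's regional inference: which regions are reported as changed by HD-tDCS and, in contrasts already labelled exploratory, whether the MCI response looks restorative or compensatory.

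**Working it through.** The plan states no map-level error rate, so there is no figure of its own to reproduce.

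**1. Where a corrected threshold is stated**

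| Effect tested | Where | Corrected threshold |
|---|---|---|
| Task | Whole brain, to define the mask | Voxel-wise FWE p<.05 |
| Any effect examined in the ROIs | Hippocampus, superior parietal lobule, caudate | Small-volume FWE p<.05 |
| Session | Inside the task mask | Not stated |
| Stimulation or group | Rest of the brain | None; uncorrected range only |

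**2. Inputs.** From the documents: p<.01 to .001, k = 10, 3 mm voxels, 5 mm kernel, at most 60 participants. The 3 mm size is stated for the normalized structural images and is taken here to hold for the second-level maps. Assumed: about 50,000–60,000 brain voxels, 20–60 participants per map, Gaussian noise, one-sided tests, and effective smoothness of 5, 6 or 8 mm. The kernel adds to the data's own smoothness, so 5 mm is the low end.

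**3. Expected noise voxels** = V × p. With V = 50,000: 50,000 × .01 = 500, and 50,000 × .001 = 50.

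**4. What k = 10 amounts to.** 10 × 27 mm³ = 270 mm³. Relative to one smoothness volume (FWHM³), that is 270/125 = 2.2 at 5 mm, 270/216 = 1.25 at 6 mm and 270/512 = 0.53 at 8 mm. A fixed k = 10 therefore loses its force as smoothness rises.

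**5. Null simulation.** Ellipsoid of 55,376 voxels, 18-connected clusters of at least 10 voxels, n = 20, 30, 40 and 60, 200 maps per cell. The first three columns give the share of maps with at least one false cluster.

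| Smoothness | p<.01 | p<.005 | p<.001 | Mean false clusters at p<.01 |
|---|---|---|---|---|
| 5 mm | 93–96% | 28–43% | 0–1% | 2.6–3.2 |
| 6 mm | 100% | 89–94% | 5–10% | 8.5–9.3 |
| 8 mm | 100% | 99–100% | 43–58% | 16.3–17.2 |

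Smaller repeat runs gave 92–98% (p<.01) and 0–3% (p<.001) at 5 mm, and 100% and 45–53% at 8 mm.

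**6. If the same range were used inside the task mask** (assumed 2,007 or 8,024 voxels, n = 30): at 5 mm, 4.5% or 28% of maps at p<.01 and 0% at p<.001; at 8 mm, 46% or 95%, and 2% or 11.5%.

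**7. The beta ANOVA, by what it might test**

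- *The effect that selected the cluster.* Take a within-person contrast with mean m and SD s at each voxel. If every voxel has m ≥ c·s, with c = t*/√n, then the cluster mean of m is at least c × the mean of s. The SD of the averaged beta is at most the mean of s. So the cluster's t is at least t*, and passing .05 is guaranteed. This follows from the algebra and adds no evidence.
- *A group difference in stimulation effect, in voxels found in one group.* Selection inflates the effect in that group only, which favours a false difference. In a 500-voxel region with the same true effect in both groups, the false-difference rate among runs with FWE survivors ranged from 8% to 99%. It depended heavily on the variance shared across voxels, for which the documents give no value. This shows direction; it is not an estimate for this trial. Whole-ROI means stayed at 3.5–7.1%.
- *An effect thought orthogonal to selection* (group-by-condition in voxels picked on the pooled effect). Error was 4.7–12.2% with FWE survivors, highest at 15 per group. With groups of 10 and 20 it was 9–52% if the selecting contrast weighted the groups equally, against 4–9% if it weighted by subject.

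**The case against.** The plan is not wholly uncorrected. *Initially* suggests a first-pass display threshold, and the mask and small-volume steps are proper FWE procedures. Survivors of FWE correction are a natural reading of the sentence on betas; on that reading, retesting the selecting effect would be redundant rather than inflating. At the only smoothing the documents give, p<.001 yields almost no false maps, so failure there needs extra smoothness that has to be assumed. The two between-group contrasts carry an exploratory label, and neither is a group-by-condition test in regions found in one group.

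Most of this stands, and it rules out some stronger readings. A reader might infer that the beta ANOVA is circular, or that its false-positive rate is near 100%. The text permits that use but does not state it. A reader might also infer that the threshold was picked after the maps were seen; the past tense shows that analyses had been run, not how the value was chosen.

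The omission is not answered. No passage converts the first-pass range into a final rule, sets a threshold inside the mask, or excludes uncorrected clusters from the beta step. The active-versus-sham contrast serves Aim 2 and has no exploratory label.

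**Conclusion.** The concern holds as an omission and should be fixed. Certainty is high that the threshold rule, the route and the tested effect are missing. It is lower for the error rates, which rest on the assumed voxel count, number scanned and, above all, effective smoothness. The contrast within the stated range is robust: at p<.01 a false cluster is close to certain at every smoothness tried, while at p<.001 the share of maps with one runs from near zero at 5 mm to about half at 8 mm. Hence k = 10 does not by itself control error even at the strict end.

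For the beta ANOVA, the documents support only that misleading uses are not excluded. Orthogonality should not be offered as a general safeguard in voxel-selected regions, since the plan fixes no HC:MCI split and error exceeded nominal even with equal groups.

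The scope is regional fMRI inference for Aim 2. Nothing here bears on the repeated-measures ANOVA for Aim 1, and it does not show that any particular reported region is false.

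**What to change.** 1. **One corrected whole-brain rule.** Replace the range with either voxel p<.001 plus cluster-level FWE p<.05, or the voxel-wise FWE p<.05 the plan already uses elsewhere. Apply voxel-wise FWE p<.05 to the tests inside the task mask. Label any uncorrected result exploratory.
2. **Define the beta step.** State which route *surviving* refers to and which effects are tested. Use betas from selected clusters descriptively only. Base inferential ANOVAs on mean betas of the whole a priori ROIs or of the whole task mask. Test group differences elsewhere with the group-by-stimulation-condition contrast at the threshold in (1).
3. **Name the factor.** Write stimulation condition (active vs sham) where that is meant. *Study Procedures* uses sessions 1 and 2 for visits whose active/sham order is counterbalanced, so a session effect read literally would test visit order.

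The cost is a change of wording, plus re-running or relabelling second-level maps already made. No new data are needed. The price is fewer regions called significant, and whole-ROI means will dilute focal effects.

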**Title: Enhancing Spatial Navigation using Non-Invasive Brain Stimulation
NCT01958437**

PI: [name], ABPP/CN

Objectives: Remembering how to travel from one location to another is critical in everyday life, yet this vital ability declines with normal aging and can be further affected by conditions that disproportionately affect older adults, such as progressive dementia. Human and animal research has shown that two distinct memory systems interact during navigation. The first, referred to as allocentric navigation, is flexible and uses spatial knowledge of key features or landmarks to develop and use a mental map of the environment. This approach involves brain regions that are critical for new learning and memory but that decline with age. The second, referred to as egocentric navigation, is inflexible and relies on “habit” memories that link specific features with specific directions. This approach relies on brain regions that are critical for “automatic” responses and that are relatively unaffected by age.

The main problem is that allocentric navigation declines with age and is accompanied by increased dependence on egocentric navigation. This change increases the risk of becoming disoriented or “lost” when traveling in unfamiliar areas or even when traveling new routes in familiar areas. Therefore, **the main goal** of this project is to examine whether non-invasive brain stimulation, specifically transcranial direct current stimulation, can improve allocentric navigation in cognitively intact older adults and those who have been diagnosed with mild cognitive impairment (MCI) – a clinical precursor to Alzheimer’s type dementia.

Specific Aims/Hypotheses:

Specific Aim 1: Examine the effects of high definition tDCS (HD-tDCS) on both allocentric and egocentric memory test performance. We predict that participants will perform more accurately following active HD-tDCS when compared to sham HD-tDCS.

Specific Aim 2: Examine the neurophysiologic response to HD-tDCS using fMRI. We predict that active HD-tDCS will increase BOLD signal in a behaviorally meaningful way regardless of diagnostic group (i.e., healthy control vs. MCI). Critical questions about the restorative vs. compensatory effects of tDCS in those with MCI will be examined by contrasting BOLD signal change between the groups

Methodology

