Participants: We will enroll up to 60 older adults (age 50+), who are right handed and MRI compatible, from the VA Ann Arbor Healthcare System, the University of Michigan Alzheimer’s Disease Center (MADC), and the surrounding community. Enrollment is open to participants regardless of race, gender, or social status.

Inclusion criteria: Patients will receive a diagnosis of MCI based on the Albert et al. (2011) criteria. Specifically, patients will **1)** report a subjective decline in memory (report can also be provided by an informant), **2)** demonstrate objective impairment in memory (based on Neuropsychological testing), and **3)** remain independent in activities of daily living. All patients will be stable on nootropic medications for at least 1-2 months prior to study initiation.

By definition, healthy controls (HC) will be free of objective memory test impairment (i.e., all scores within normal limits on the standardized testing protocol below).

Exclusion criteria: A history of **1)** contributory other neurological (e.g., epilepsy, moderate - severe traumatic brain injury) or medical conditions that are known to affect cognitive functioning; **2)** significant psychiatric conditions (e.g., moderate - severe depression, bipolar disorder, schizophrenia); **3)** sensory impairments that limit the ability to take part in the study; **4)** a significant history or current use of alcohol or drug abuse/dependence. Participants will also be screened to ensure MRI compatibility (assessed using the guidelines set forth by the American College of Radiology); some of the criteria for which are also reasons for excluding someone from tDCS (e.g., metallic or electronic implants). Eligible participants who cannot undergo MRI will be enrolled in the study and will complete only the stimulation and behavioral portions of the study. We have successfully used this same approach in our previous RCTs.

Recruitment: Participants will be recruited from both the VA Ann Arbor Healthcare system and the University of Michigan Alzheimer’s Disease Center. The primary recruitment source of MCI patients at the VA will be the Neuropsychology Clinic while HC will be recruited from the general VA community via postings/flyers in approved areas. The primary recruitment site for non-Veterans will be the University of Michigan Alzheimer’s

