Disease Center (MADC). The MADDC recruits participants from several sources including its memory disorders clinic, community screening events, and external referrals. Participants interested in research are maintained in an IRB-approved database, which is available to the PI and his study team. This database includes individuals who are cognitively intact (HC) and those with MCI.

Screening & Cognitive Assessment: After providing informed, written consent, participants will undergo a brief neuropsychological protocol to ensure they continue meeting MCI criteria as outlined above (for patients) or that they are, in fact, cognitively intact (for the HC). This protocol includes standardized measures that are shown in the table below. Other measures may be added to the protocol to characterize the nature of the patient's cognitive functioning as necessary. Participants will be given breaks as necessary to ensure their comfort and are allowed to discontinue at any point for any reason.

Measure	Description	Screening Session
Montreal Cognitive Assessment (MOCA)	Gross screening measure for overall cognitive functioning (~5 minutes)	X
Wechsler Test of Adult Reading (WTAR)	Single word reading – used to establish premorbid intellectual estimates (~3 minutes)	X
Repeatable Battery for the Assessment of Neuropsychological Status (RBANS)	Brief Neuropsychological battery that includes Indices of attention, visuospatial, learning, memory, and processing speed. (~20 minutes)	X
Emory short version of Wisconsin Card Sorting Test (WCST)	Assesses the ability to identify possible solution strategies and abstract problem solving (~5-15 minutes)	X
Trail Making Test	Measures of psychomotor processing (Trails A) and set shifting (Trails B) (~3-10 minutes)	X
Temporal Sequencing Task	Novel Temporal Memory Task (~5 minutes)	X
Functional Activities Questionnaire (FAQ)	Evaluates patient's ability to perform everyday tasks (i.e., ADLs/IADLs) (~3 minutes)	X
Geriatric Depression Scale (GDS)	Evaluates current symptoms of depression (~3 minutes)	X
Multifactorial Memory Questionnaire (MMQ) & Memory Assessment Clinics – self report (MAC-S)	Self-report questionnaires that assess perceived memory complaints (~15minutes)	X
Object Location Touchscreen Test (OLTT)	Assesses the ability to learn and remember the location of objects (~10 minutes)	X
Screening protocol.		

Eligible participants move forward into the study, details of which are provided below.

Study Procedures:

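### The exploratory HC-versus-MCI fMRI contrasts are neither matched nor adjusted for age, so reading them as disease-related is not secured by the plan

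*Combined protocol and SAP*

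**What the plan says.** - **Age rule (Participants).** "We will enroll up to 60 older adults (age 50+), who are right handed and MRI compatible". No upper limit and no split between the groups is given. HC are defined by normal test scores alone. No section matches, stratifies or balances HC to MCI on age, sex or education.
- **Routes (Recruitment).** At the VA they differ: "The primary recruitment source of MCI patients at the VA will be the Neuropsychology Clinic", whereas "HC will be recruited from the general VA community via postings/flyers in approved areas". For non-Veterans the main source is the MADC database, and "This database includes individuals who are cognitively intact (HC) and those with MCI".
- **Randomisation (Study Procedures).** Only the order of active and sham is randomised, separately within each diagnostic group.
- **Covariates.** Statistical Design allows unnamed, optional confounders in the behavioural ANOVA. For fMRI, Task analysis names six motion parameters at first level, and task, session and group at second level. The second-level models under Resting state analysis name no covariate.
- **Interpretation.** The exploratory between-group paragraph that closes the analysis text says of contrast 1 (HC sham > MCI sham) "which will identify disease-related differences in activation between the groups". Contrast 2 (HC active > MCI active) is to show whether stimulation-related change is larger in one group. The two together are to separate restoration from compensation.
- **Premise (Objectives).** "The main problem is that allocentric navigation declines with age". The same section says that the brain regions behind allocentric navigation also decline with age.

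**The concern.** HC versus MCI is a comparison between different people that randomisation does not protect. The protocol itself names age as a cause of lower function in the regions under study, then leaves age out of both the selection of controls and the group model. If the MCI participants turn out to be older, the model as written assigns the age part of any activation difference to diagnosis. Regions would then be labelled disease-related, and used as the benchmark for normal navigation, partly because of age. Specific Aim 2 treats the restorative-versus-compensatory question as critical and answers it by contrasting the groups, so the interpretation matters even though these contrasts are labelled exploratory.

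**Working it through.** The documents give no ages, SDs, effect sizes or power calculation, so there is no stated figure to reproduce. The check has two parts.

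**1. Is age handled anywhere?** The optional covariate sentence belongs to the behavioural ANOVA. The first-level motion parameters vary within a person's scan and do not represent age. The closing allowance for additional analyses concerns tDCS-related change and names no covariate. Nothing in the text therefore controls age in the HC-versus-MCI contrasts.

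**2. How large could the effect be?**

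Input from the documents: at most 60 participants; whole-brain maps thresholded at p < .01 to .001 uncorrected; extracted beta values tested at p < .05.

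Assumptions: 30 per group (an even split of the maximum); within-group age SD *s* = 8 years; correlation of age with activation *r* = 0.3 in magnitude, activation falling with age; MCI older by *g* years; no true disease effect.

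Formulas: spurious standardised difference d = r × g / s; noncentrality = d × √(n/2), with √(30/2) = 3.873; noncentral t with 2n − 2 = 58 df.

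| g (years) | d | Noncentrality | Two-sided .05 | One-sided .01 | One-sided .001 |
|---|---|---|---|---|---|
| 0 | 0 | 0 | 5.0% | 1.0% | 0.10% |
| 3 | 0.3 × 3/8 = 0.113 | 0.44 | 7.1% | 2.9% | 0.38% |
| 5 | 0.3 × 5/8 = 0.188 | 0.73 | 11.0% | 5.3% | 0.84% |
| 5.5 | 0.3 × 5.5/8 = 0.206 | 0.80 | 12.3% | 6.1% | 1.0% |
| 8 | 0.3 × 8/8 = 0.300 | 1.16 | 20.8% | 11.7% | 2.4% |

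A normal approximation puts the 5.5-year two-sided rate at 12.6%. These are rates for a single voxel or region before any multiplicity correction.

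Sensitivity: with r = 0.2 and a 3-year gap, the two-sided rate is 5.9%, barely above nominal. With 15 per group, r = 0.3 and a 5-year gap, it is 7.9%, and the one-sided .01 rate is 3.3%.

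**Effect of adding age.** In a 20,000-run simulation (30 per group, r = 0.3, 5-year gap), the two-sided .05 rate was 11.1% without age and 4.9% with it. The one-sided .01 rate was 5.5% without and 1.0% with.

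**Precision cost of age.** Variance inflation at a 5-year gap is 1 + (5/8)²/4 = 1.098. Age removes a fraction 0.3² = 0.09 of residual variance. The net SE factor is √(0.91 × 1.098) = 1.00. At an 8-year gap it is √(0.91 × 1.25) = 1.07.

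**What cancels.** Suppose age adds the same offset A to the HC − MCI difference in both sessions. Contrast 1 is then the true difference plus A, and so is contrast 2. Subtracting contrast 1 from contrast 2 removes A, so the group-by-session change is free of it.

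**The case against.** The strongest reply is that no confounding has been shown. A reader might infer from the open age range and the unmatched groups that the contrasts are in fact confounded. The documents do not support that: no ages are reported, and equal mean ages would make the bias zero. This stands, and the point is limited to lack of protection.

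A reader might also infer that the groups come from different sources throughout. That is true only at the VA. The MADC database supplies both groups, although sharing a database does not equalise their ages.

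Large inflation figures are tempting but selective. A rate near 21% needs the full 8-year gap. The imaging sample may also be below 30 per group, because 60 is a ceiling and Exclusion criteria lets participants who cannot have MRI complete only the stimulation and behavioural parts. Smaller groups reduce the inflation. The two-sided .05 level applies to extracted betas that have already survived earlier thresholds, not to the whole-brain maps. All of this stands.

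It could further be said that the restoration-versus-compensation reading is safe because the two contrasts are read together and group and session share one mixed ANOVA. This holds in part. An additive offset cancels from the change between sessions, but each contrast read alone remains exposed. Contrast 2 has no sham subtraction, although it is described as addressing tDCS-related change.

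The exploratory label lowers the stakes. It does not justify a causal label on an unadjusted group difference.

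**Conclusion.** The concern holds in a limited form. The plan neither prevents nor adjusts for age confounding in the HC-versus-MCI fMRI contrasts, while reading contrast 1 as disease-related. The actual bias is unknown. Under the stated assumptions a gap of 5 to 5.5 years roughly doubles the two-sided 5% error and raises the one-sided .01 error five- to sixfold; with no gap there is no inflation.

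The exposure covers contrast 1 and contrast 2 when each is read alone. It does not extend to the within-person active-sham tests, and a reader should not infer that the evidence for a stimulation effect is weakened. The group-by-session change is also unaffected by an additive age offset. The correction is worth making because it is nearly free and the between-group reading serves Specific Aim 2.

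**What to change.** 1. In Task analysis, Resting state analysis and the between-group paragraph, state that all HC-versus-MCI contrasts, task and resting state, include mean-centred age and sex as second-level covariates.
2. Report age, sex and education by group, with a check that the age ranges overlap.
3. Add WTAR (already in the screening protocol) and recruitment source (VA or MADC) as a sensitivity analysis.
4. Describe contrast 1 as an age-adjusted group difference instead of disease-related.
5. Frequency-matching HC to MCI on age is optional and possible only if enrolment is still open. Much of the imaging text is in the past tense, so it may be too late.

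Cost: about 2 degrees of freedom (58 to 56 with 30 per group), and reliance on a linear age slope common to both groups, which is why the overlap check is needed. Age has to be known already to apply the 50+ rule. No extra participants or procedures are required.
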